Abnormalities in myocardial energy metabolism constitute a crucial pathological basis for heart failure, with mitochondria playing a pivotal role as the primary site for ATP production. Elucidating the role of mitochondrial energy metabolic remodeling in the pathogenesis of different types of heart failure and its potential for therapeutic intervention could facilitate the early identification of risk factors for heart failure and lead to more effective improvements in prognosis. Our previous research has focused on mitochondria in failing myocardium, and through proteomic analysis, we have identified nearly a hundred differentially expressed mitochondrial proteins, including aldehyde dehydrogenase 2 (ALDH2). ALDH2 is a key enzyme involved in mitochondrial glycolipid metabolism[4], possessing a redox-sensitive

thiol group at its active site. An increase in endogenous oxygen free radicals promotes the formation of disulfide bonds at the ALDH2 active site, leading to its inactivation [5]. Given the abundant distribution of this enzyme in the myocardium, we have conducted a series of studies on the role of ALDH2 in myocardial injury and protection. Our findings indicate that ALDH2 exerts cardioprotective effects by maintaining mitochondrial metabolic homeostasis under cardiovascular pathological stimuli such as ischemia, hypoxia, and alcohol exposure [6-12]. Furthermore, we have demonstrated that ALDH2 is a prerequisite for enhancing the therapeutic efficacy of stem cell transplantation in the treatment of heart failure [13-14]. Our research has pioneered international efforts in confirming the significant advantages of ALDH2 in preventing cardiovascular diseases and diabetes, sparking a global research fervor into the protective effects of ALDH2 in various disease contexts. Additionally, our findings have garnered international attention regarding ALDH2 as a potential target for drug development. The significance of ALDH2 in numerous human diseases is gradually being elucidated, with substantial evidence from domestic and international peers indicating its irreplaceable role in preventing other cardiovascular diseases, cerebrovascular diseases, hematological disorders, and malignant tumors, among others [15-18]. Autologous bone marrow-derived aldehyde dehydrogenase-bright (ALDH^{br}) cells, which express highly active ALDH2, have been proven safe and effective in patients with chronic myocardial ischemia [19]. Given its pivotal role in cellular protection and its significance in various human diseases, ALDH2 may represent a novel therapeutic target for the treatment of multiple diseases [20-21].

Lipoic acid (LA), a vitamin B-class compound, features a closed cyclic structure composed of sulfur and carbon atoms, conferring relatively high electron density and thus strong antioxidant properties. LA

has demonstrated favorable preventive and therapeutic effects on diabetes and its complications, various brain and neurodegenerative diseases, and aging [22-24]. The role of LA in cardiovascular diseases has increasingly attracted attention, with studies confirming that LA can restore ALDH2 activity by reducing disulfide bonds at its active site in mitochondria, thereby enhancing nitrate tolerance [25]. Subsequently, scholars have discovered that lipoic acid (LA) also exerts protective effects on diabetic cardiomyopathy and acute ischemia-reperfusion injury by restoring the activity of ALDH2 [26-28]. Given the protective role of ALDH2 in ischemic heart failure and the ability of LA to reduce ALDH2 activity, we propose the following scientific hypothesis: during the recovery phase of post-ischemic heart failure, lipoic acid can improve myocardial mitochondrial energy metabolism and inhibit oxidative stress by reducing the activity of ALDH2 in myocardial mitochondria, thereby protecting against post-ischemic heart failure. Currently, due to its potent antioxidant properties and rare adverse effects, lipoic acid has been widely promoted for clinical use. Clinically available forms of lipoic acid include intravenous injections and oral capsules, with indications for sensory abnormalities caused by diabetic peripheral neuropathy. Adverse reactions are extremely rare, with an incidence rate of <1/10,000, primarily manifesting as gastrointestinal symptoms such as nausea and vomiting, cutaneous allergic reactions, abnormal taste perception, or hypoglycemia.

This study employs a prospective, multicenter, randomized, and controlled research design to assess the clinical outcomes of patients with heart failure following myocardial infarction (MI) who are treated with a combination of lipoic acid capsules and standard pharmacological therapy. The evaluation will be conducted using a range of indicators, including primary endpoint events, secondary endpoint events, control of risk

factors, and surveys on medication adherence. The primary objective is to elucidate the significant role of lipoic acid capsules in managing post-MI heart failure, thereby paving the way for innovative approaches in heart failure treatment.

This structured approach ensures a rigorous and comprehensive assessment, allowing us to draw meaningful conclusions about the efficacy and safety of lipoic acid capsules in this patient population. By integrating multiple evaluation metrics, we aim to provide a holistic view of the treatment's impact on patient outcomes, ultimately contributing to the advancement of evidence-based practices in heart failure management.

二、 Objectives

The clinical outcomes of lipoic acid capsules combined with standard pharmacological therapy in patients with heart failure following myocardial infarction are evaluated through indicators such as primary endpoint events, secondary endpoint events, control of risk factors, and surveys on medication adherence.

三、 Protocol

3.1 Design

This is a multicenter, double-blind, randomized, placebo-controlled, parallel-group, exploratory trial.

3.2 Population

Inclusion criteria: 1. Patients aged 18 years or older who had been diagnosed with acute myocardial infarction (AMI) for more than 30 days. The diagnosis of AMI was based on the Fourth Universal Definition of Myocardial Infarction, which encompassed clinical evidence of acute

myocardial ischemia and with detection of a rise and/or fall of cardiac troponin (cTn) values, with at least 1 value above the 99th percentile upper reference limit (URL) and at least 1 of the following: symptoms of myocardial ischemia; new ischemic electrocardiogram changes; development of pathological Q waves; imaging evidence of new loss of viable myocardium or new regional wall motion abnormality in a pattern consistent with an ischemic etiology, identification of a coronary thrombus by angiography; 2. Patients were diagnosed with chronic heart failure (NYHA class II-IV) with a documented LVEF \leq 50%. The diagnosis of chronic heart failure was based on the global definition[16]: Symptoms and signs of HF with elevated natriuretic peptides (BNP) (NTproBNP $>$ 600pg/ml or BNP \geq 150pg/ml; NT-proBNP \geq 400 pg/mL or BNP \geq 100 pg/mL, if patients were hospitalized for heart failure within 12 months; 3. The patients were clinically stable and had received optimal medical treatment with a fixed dosage for at least 4 weeks; 4. Patients were fully informed about this study and provided written informed consent.

Exclusion criteria: patients who were allergic to drugs of similar chemical classes (Vitamin B) as well as known or suspected contraindications to the study drugs; already used other investigational drugs at the time of enrollment, or within 30 days or over 5 half-lives of the drug prior to enrollment; with a history of intolerance to recommended target doses of ALA; have been diagnosed with acute decompensated HF (exacerbation of chronic HF manifested by signs and symptoms that may require intravenous therapy); with systolic blood pressure $<$ 100 mmHg; severe liver function abnormalities (alanine aminotransferase (ALT) or aspartate aminotransferase (AST) more than 3 times the upper limit of normal); an estimated glomerular filtration rate (eGFR) $<$ 30 mL/min/1.73m², as measured by the simplified MDRD

formula; a serum potassium > 5.2 mmol/L; were pregnant or planning to become pregnant.

Withdrawal criteria: 1. The participant themselves requests to withdraw from the trial; 2. The participant experiences an intolerable adverse event, or an adverse event that, in the investigator's opinion, necessitates withdrawal from the study; 3. The participant is unable to adhere to the study protocol for treatment, demonstrates poor compliance, or is deemed by the physician to be unsuitable for continued participation in the study group.

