3.5.2 Follow-up Period

Patients underwent baseline visits on Day 0 post-randomization, followed by visits at Months 6, 12, and 24, totaling 4 on-site visits for efficacy, compliance, and safety assessments until study completion. The follow-up period lasted 24 months.

Visit 1 (Screening and Enrollment Period)

Inclusion and exclusion criteria

Informed consent signing

Past medical history and comorbidities

Comprehensive physical examination

Detailed documentation of medical history, comorbidities, treatment, concomitant medications, blood pressure, heart rate, weight measurement.

Cardiac function assessment (6-minute walk test: 6MWD)

Electrocardiogram (ECG)

Echocardiography

Laboratory tests: blood/urine/biochemical parameters, brain natriuretic peptide (BNP), coagulation function

Distribution of study medication

Instructions for the next follow-up visit date and brief physical examination

Visit 2 (Month 6 post-randomization), Visit 3 (Month 12 post-randomization), Visit 4 (Month 24 post-randomization)

Heart failure symptoms and signs

Comprehensive physical examination

Blood pressure, heart rate, weight measurement

Documentation of primary and secondary endpoint events

Adverse event recording

Cardiac function assessment (6MWD)

ECG

Echocardiography

Laboratory tests (blood/urine/biochemical parameters, BNP), coagulation function

Distribution/collection of study medication

Instructions for the next follow-up visit date or study termination

During months without on-site visits, researchers should contact patients via telephone to inquire about adverse events, endpoint events, and changes in concomitant medications, completing corresponding records.

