3.6 Study Endpoint

3.6.1 Primary Endpoint:

A composite endpoint of all-cause death and rehospitalization due to heart failure during the 24-month follow-up period.

3.6.2 Secondary Endpoints:

The second endpoints included all-cause death and rehospitalization due to heart failure, non-fatal MI or non-fatal stroke during the 24-month follow-up period. The changes of LVEF and 6MWD were also assessed from baseline to 24 months.

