4.4 Risk Prevention and Management

The investigator should assess the clinical significance of abnormal laboratory results and provide possible explanations. Laboratory abnormalities resulting from previously reported adverse events should

also be recorded as adverse events in the Adverse Event Form. Laboratory abnormalities with clinical significance that meet one or more of the following criteria should be recorded as independent diagnoses in the Adverse Event section of the CRF (excluding abnormalities resulting from previously reported adverse events):1.Accompanied by clinical symptoms ; 2.Leading to changes in clinical medication ; 3.Requiring modification of concomitant therapy.

For unexplained abnormal laboratory values, repeat testing should be performed, and follow-up should continue until the value returns to the normal reference range or baseline, and/or a reasonable explanation is found. If a clear explanation is identified, it should be documented on the CRF.

During the clinical trial, investigators should closely monitor the occurrence of serious adverse events. Upon the occurrence of a serious adverse event, necessary measures should be taken first to ensure the safety of the subject, followed by reporting to the sponsor, contract research organization (CRO), and the ethics committee of the center within 24 hours.

All safety follow-up visits will be conducted 15 days after the end of the study visit. For subjects who withdraw prematurely, safety follow-up will also be conducted 15 days after the end of the study visit, unless the investigator deems it necessary for the subject to return to the hospital for follow-up measurements due to persistent adverse events at the end of treatment or clinically significant abnormalities in laboratory tests or vital signs. Safety follow-up may be conducted via telephone.

五、 Statistic Method

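### The withdrawal criteria let adverse events or poor compliance end study participation, and nothing says that deaths and HF admissions are still collected to month 24

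*Protocol*

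**What the plan says.** Section 3.2 has a single list of withdrawal criteria. Item 1 is the participant's own request. Item 2 covers intolerable adverse events and any adverse event that, in the investigator's view, "necessitates withdrawal from the study". Item 3 reads "The participant is unable to adhere to the study protocol for treatment, demonstrates poor compliance", and adds patients whom the physician judges "unsuitable for continued participation in the study group". The list does not distinguish stopping the capsules from leaving follow-up.

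Only section 4.4 says what happens after premature withdrawal: "For subjects who withdraw prematurely, safety follow-up will also be conducted 15 days after the end of the study visit". The same section gives that contact to everyone: "All safety follow-up visits will be conducted 15 days after the end of the study visit".

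Section 3.5.2 sets visits at baseline and months 6, 12 and 24, "totaling 4 on-site visits for efficacy, compliance, and safety assessments until study completion". In the other months, "researchers should contact patients via telephone to inquire about adverse events, endpoint events, and changes in concomitant medications". Neither sentence mentions withdrawn patients.

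The primary endpoint in section 3.6.1 is "A composite endpoint of all-cause death and rehospitalization due to heart failure during the 24-month follow-up period". Section 5.1 assumes a fixed 24-month follow-up and 5% withdrawal in both groups, without saying whether that 5% stop drug or leave follow-up. Sections 5.2.2 and 5.2.3 state the intention-to-treat principle, although 5.2.2 also requires at least one month of drug use for the full analysis set.

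**The concern.** Tolerability and compliance are post-randomisation matters. If they take a patient out of the study and not only off the drug, later deaths and heart failure admissions are not collected. The Kaplan-Meier and Cox analyses then censor that patient at withdrawal, for a reason that may be related to prognosis. No analysis plan can recover events that were never recorded, so this is a matter for the protocol.

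Two results are exposed. One is the hazard ratio. The other is the 24-month event rate, which section 5.1 wants as reference data for a later, larger trial. Four centres will apply section 3.2, and they could read it differently.

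**Working it through.** **Reading the sections together.** Item 2 makes study exit a consequence of an adverse event, and item 3 does so for poor compliance. The endpoint window (3.6.1), the fixed follow-up (5.1) and the intention-to-treat principle (5.2.3) all need events to month 24 whatever the drug status. Section 3.5.2 could supply them but does not say that it covers withdrawn patients. Section 4.4 neither ends nor extends endpoint collection, because completers get the same 15-day contact.

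**Inputs from section 5.1.** 150 per arm, control risk 35% at 24 months, HR 0.60, 5% withdrawal per arm, two-sided alpha 0.10, stated power 80%.

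**The plan's own figure.**
- ALA risk = 1 − 0.65^0.60 = 22.8%.
- Events = 150 × (0.350 + 0.228) = 86.7.
- Schoenfeld power = Φ(√86.7 × |ln 0.60|/2 − 1.645) = Φ(0.733) = 76.8%. Freedman's formula gives 75.3%.

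The stated 80% is not reproduced. That is a separate matter, but it is why the power figures below start near 76%.

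**Assumptions for the size.** Event times are exponential. A share f = 5% of each arm has k times the hazard λ of the other patients, with λ set so that the overall control risk stays 35%. Only these patients withdraw, and they are censored at withdrawal, uniformly over months 1–12 or over months 0–24. The documents give no value for k, so the range is 0.5 to 3.

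**Events lost.** For k = 1, λ = −ln(0.65)/24 = 0.01795 per month, and 0.60 × λ = 0.01077 in the ALA arm. In each arm 0.05 × 150 = 7.5 patients withdraw, on average at month 6.5 when withdrawal falls in months 1–12:
- Control: 7.5 × (e^(−0.01795×6.5) − 0.65) = 7.5 × (0.890 − 0.650) = 1.8
- ALA: 7.5 × (e^(−0.01077×6.5) − 0.772) = 7.5 × (0.932 − 0.772) = 1.2
- Total 3.0, as in the table.

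**Control Kaplan-Meier rate.** With G(t) the share of the withdrawing group still followed at time t, the observed hazard is h(t) = [(1−f)λe^(−λt) + f·kλe^(−kλt)G(t)] / [(1−f)e^(−λt) + f·e^(−kλt)G(t)], and the estimated rate is 1 − exp(−∫h dt) over 0–24 months. Power is by simulation at HR 0.60 and two-sided 0.10.

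Each cell gives months 1–12 / months 0–24:

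| k | Control rate (true 35%) | Events lost of about 87 | Power: full follow-up → censored |
|---|---|---|---|
| 0.5 | 35.6% / 35.4% | 1.7 / 1.2 | 76.2% → 75.5% / 75.7% |
| 1 | 35.0% / 35.0% | 3.0 / 2.0 | 76.2% → 74.9% / 75.4% |
| 2 | 34.2% / 34.5% | 4.8 / 3.2 | 75.9% → 74.2% / 74.7% |
| 3 | 33.8% / 34.2% | 5.8 / 3.8 | 75.1% → 73.6% / 74.2% |

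**Hazard ratio.**
- No treatment effect, 5% in each arm, same kind of patient leaving: HR 1.00, and 2.3% to 2.5% significant results favouring ALA at a two-sided 0.05 test (nominal 2.5%).
- No treatment effect, 5% in each arm, but ALA loses only patients at three times the hazard and placebo only patients at half the hazard: HR 0.94; with the arms reversed, 1.06. This is an extreme case. It shows that equal rates alone do not protect the HR.
- Benefit stops with the drug: 5% of the ALA arm withdraw at month 6 and return to the control hazard. ALA risk = 0.95 × 0.2278 + 0.05 × (1 − e^(−0.01077×6 − 0.01795×18)) = 0.2164 + 0.0161 = 0.2325. HR with full follow-up = ln(0.7675)/ln(0.65) = 0.61, against 0.60 if they are censored.

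**The case against.** The strongest reply is that the protocol, read as a whole, already implies follow-up to month 24. Visits run to study completion, calls about endpoint events fill the other months, follow-up is fixed, and the analysis claims intention to treat. Nothing says that later events are discarded. This stands in part: the general sections do lean that way. But they do not mention withdrawn patients, while section 3.2 does, and its words point to leaving the study.

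A reader might infer from section 4.4 that endpoint collection stops 15 days after withdrawal. The text does not support this, because completers get the same contact.

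The second reply is size. At 5% per arm the losses are small, and if the 5% in section 5.1 means leaving follow-up, some or all of the power loss is already allowed for. This stands.

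A reader might also infer a material bias in favour of ALA. With 2% withdrawal on placebo and 10% on ALA, all at three times the hazard, the HR under no effect would be about 0.94. The documents give no support for those inputs. Section 5.1 plans 5% in both groups, the capsules are identical and blinded, and the background section puts adverse reactions below 1 in 10,000. With the arms reversed the bias turns the other way (1.07).

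**Conclusion.** The point holds as a gap with a small expected effect and a cheap remedy. Section 3.2, followed as written, can end endpoint collection for post-randomisation reasons, and no other section prevents it.

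At the planned 5% per arm, about 2 to 6 of 87 events would go uncollected at one to three times the hazard of the other patients (1 to 2 at half). Power would fall by 0.5 to 1.7 points, and the control rate would be estimated at 33.8% to 35.6% against 35%. That estimate is unbiased if withdrawn patients have average risk, too low if their risk is higher, and too high if it is lower.

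The hazard ratio can be biased if the rate or the kind of withdrawal differs between arms, or if the treatment effect ends with the drug. The documents give neither the prognosis of withdrawn patients nor any imbalance, so the direction is unknown. All sizes rest on the 5% and on the assumed hazards and timing. They grow if more patients leave follow-up, and item 3 sets no threshold for poor compliance.

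**What to change.** Reconcile section 3.2 with sections 3.5.2, 3.6.1, 5.1, 5.2.2 and 5.2.3:

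- State that stopping study drug under item 2 or 3 does not end follow-up. Every randomised patient is followed for death, heart failure hospitalisation, MI and stroke to month 24, through the visits and calls already in 3.5.2, unless consent to follow-up is withdrawn.
- State in section 5.1 whether the 5% means stopping drug or leaving follow-up.

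Items 2 and 3 now govern study participation, so this changes their consequence. The clinical grounds for stopping study drug should stay as they are. Section 4.4 can stand.

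Cost: an amendment with ethics approval under section 6.1, and continued contact with about 0.05 × 300 = 15 patients. That is at most 15 × (24 − 12) = 180 monthly contacts if withdrawal is spread over months 0–24, or 15 × (24 − 6.5) ≈ 260 if it falls in months 1–12. It is fewer where patients die or withdraw consent to follow-up.

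The one-month drug-use condition in section 5.2.2 is a separate departure from intention to treat that this change does not resolve.

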3.3 Number of Cases and Grouping Method

The overall trial plans to enroll 300 patients who meet the inclusion criteria, and they will be randomly assigned to either the treatment group or the control group, with 150 patients in each group. This study is a prospective, multicenter, randomized, and controlled trial. It is planned to include 100 cases from our hospital, 100 cases from Affiliated Zhongshan Hospital of Dalian University, 50 cases from the First Affiliated Hospital of Sun Yat-sen University and 50 cases from Shanxi Cardiovascular Hospital.

Randomization: The randomization method employed in this study is block randomization. The statistician generated a random number table using computer software and conducted drug blinding based on it.

Blinding Procedure: Participants who are randomly assigned to the placebo group will also take capsules that are identical in appearance to those containing lipoic acid. Investigators at each center will be unaware of the difference between the two. Under normal circumstances, the blind will be maintained until all participants have completed the study and the database has been finally locked. Emergency unblinding may only occur when the participant's treatment status is required to determine special

emergency treatment. The date, time, and reason for unblinding will be recorded in the original documents and CRF (Case Report Form) tables.

3.4 Investigational Drugs

3.4.1 Investigational Medicinal Products:

Investigational Drug: Lipoic Acid Capsules

Placebo: Contains starch as the inert ingredient, with an identical appearance to the investigational drug

3.4.2 Dosage Form, Dose, Route of Administration, Administration Method, Frequency of Administration, and Treatment Duration

Dosage Form: 100mg capsules

Dose: 600mg per day

Route of Administration: Oral

Frequency of Administration: 200mg per dose, administered three times daily

Treatment Duration: 24 months

